10. ANALYSIS POPULATIONS

Four analysis population are defined below. Number and percent of patient meeting the definition of each analysis population will be summarized by treatment group.

10.1. SCREENED POPULATION

The Screened Population will consist of all subjects who underwent a Screening Visit and received a subject identification number.

10.2. RANDOMIZED POPULATION

The Randomized Population will consist of all enrolled subjects who were randomized to a treatment group in the trial.

10.3. INTENT TO TREAT ANALYSIS SET

The Intent-To-Treat population will consist of all randomized subjects who have received any amount of the trial drug. Subjects will be analyzed by the treatment arm as randomized.

10.4. PER-PROTOCOL ANALYSIS SET

The Per-Protocol Analysis Set will be a subset of Intent to Treatment population. This set will exclude subjects with the following protocol deviation during the trial:

- Treatment Non-Compliance (Missed or overdosed) at least +/- 20 % of lonapegsomatropin, placebo, or daily somatropin doses during the treatment period
- Failed to have a DXA measurement at Week 38 visit
- Violates major inclusion or exclusion criteria (inclusion 02,03,04 or exclusion 07,15,18)
- Early termination defined as subjects who withdraw from the trial prior to Week 38 visit

- Any Prohibited therapies and procedures:
 - anti-obesity drugs/appetite suppressants (unless prescribed for indication other than weight loss/obesity)
 - GLP-1 receptor agonists (even if indicated for diabetes mellitus)
 - hGH therapies other than trial drug, GH secretagogues
 - bariatric surgery
 - anabolic steroids other than testosterone
 - cabergoline >0.5 mg/week or bromocriptine >20 mg/week (due to their effects on lowering IGF-1 and GH hormonal concentrations and their independent effects on weight)

The Per-Protocol analysis set will be used for sensitivity analysis of the primary efficacy endpoint. The Per-Protocol analysis set and the criteria will be identified prior to unblinding the trial.

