5. For subjects on hormone replacement therapies for any hormone deficiencies other than GH (eg, adrenal, thyroid, estrogen, testosterone) must be on adequate and stable doses for ≥ 6 weeks prior to and throughout screening.

Note: Short-term increases in glucocorticoid doses taken on an as-needed basis for adrenal insufficiency are permitted (“stress dose” allowance: duration up to 5 days up to 2 times in 6 weeks, the maximum dose may reach 3 times the stable dose). One-time dose increases for diagnostic or other medical procedures are allowed.

Note: For subjects receiving oral estrogen or estrogen-containing therapy, subjects must intend to maintain the same dose and route of estrogen administration throughout the trial. For subjects receiving non-oral estrogen or estrogen-containing therapy, the dose may be adjusted as required, however subjects must intend to maintain the same route of administration throughout the trial.

6. For subjects not on glucocorticoid replacement therapy, documentation of adequate adrenal function at screening defined as: morning (6:00-10:00AM) serum cortisol $>15.0 \mu\text{g/dL}$ (measured at central laboratory) and/or Adrenocorticotrophic Hormone (ACTH) stimulation test or ITT with serum cortisol $>18.0 \mu\text{g/dL}$ at or within 90 days prior to screening. Stimulation test protocols and results are subject to review and approval by the Medical Monitor.
7. For males not on testosterone replacement therapy: morning (6:00-10:00AM) total testosterone within normal limits for age as measured by the central laboratory at screening.
8. On a stable diet and exercise regime at screening with no intention to modify diet or exercise pattern during the trial, ie, no weight reduction program intended during the trial or within the last 90 days prior to or through screening.
9. No plans to undergo bariatric surgery during the trial.
10. Fundoscopy at screening without signs/symptoms of intracranial hypertension or diabetic retinopathy stage 2 / moderate or above or any other retinal disease contraindicated to growth hormone therapy. For subjects with a diagnosis of diabetes mellitus at screening, this must be documented with a fundus photograph.

11. Able and willing to provide a written ICF and authorization for protected health information (PHI) disclosure in accordance with Good Clinical Practice (GCP).
12. Serum fT4 in the normal range at screening as measured by central laboratory.

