
7. Subjects with prior cranial irradiation or hypothalamic-pituitary surgery: the procedure took place less than 12 months prior to screening.
8. eGFR <60 mL/min/1.73m² determined based on Modification of Diet in Renal Disease (MDRD) equation using serum creatinine from the central laboratory at screening.
9. Hepatic transaminases (ie, AST or ALT) >3 times the upper limit of normal according to the central laboratory at screening.
10. Heart failure NYHA class 3 or greater ([NYHA 1994](#)).
11. QTcF \geq 451 milliseconds on 12-lead ECG at screening.

Note: If the initial measurement is out of range, the assessment should be repeated 2 more times and the average QTcF value should be used to determine the subject's eligibility.

12. Poorly controlled hypertension, defined as supine systolic blood pressure >159 mmHg and/or supine diastolic blood pressure >95 mmHg at screening

Note: if the initial measurement is out of range, may be repeated 2 more times after 15 min and exclusion will be based on the average of the three measurements.

13. Cerebrovascular accident within 5 years prior to screening.
14. Anabolic steroids (other than gonadal steroid replacement therapy) or oral/intravenous/intramuscular corticosteroids (other than in replacement or stress doses as described in Inclusion Criterion No.5) within 90 days prior to or throughout screening.

Note: Stable doses of inhaled, intra-articular, or topical corticosteroids are permitted.

15. Currently using or have used within 26 weeks prior to screening any weight-loss or appetite-suppressive medications including orlistat, zonisamide, lorcaserin, bupropion, topiramate, sibutramine, stimulants (eg, phentermine or ADHD medications such as methylphenidate or amphetamines), GLP-1 receptor agonists (eg, dulaglutide, exenatide, liraglutide, lixisenatide, semaglutide), SGLT-2 inhibitors (eg, canagliflozin, dapagliflozin, empagliflozin, sotagliflozin) or medications that affects IGF-1 or GH measurements including cabergoline at doses above 0.5 mg weekly or bromocriptine at doses above 20 mg weekly.

Note: if it can be documented that no weight-loss occurred with these drugs, a 90-day withdrawal period prior to screening is sufficient.

16. Known history of hypersensitivity and/or idiosyncrasy to any of the test compounds (somatropin) or excipients employed in this trial.
17. Known history of neutralizing anti-hGH antibodies.
18. Inability to undergo scanning by DXA or a non-interpretable DXA scan at screening.

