9.9.2.1. Permitted Therapies

Therapies not listed as prohibited therapies are allowed when taking the precautions in this section into consideration.

Somatropin administration may increase the clearance of compounds known to be metabolized by cytochrome P450 isoenzymes.

Therefore, the clearance of compounds such as sex steroids, corticosteroids, anticonvulsants, and cyclosporine may be especially increased resulting in lower plasma levels of these compounds.

- Replacement therapy for other non-GH pituitary deficiencies. As hGH may enhance the transformation of hydrocortisone to cortisone, the investigator may increase the dose of hydrocortisone replacement therapy if needed (eg, for anticipated stress). As hGH may increase extrathyroidal conversion of T4 to T3, the investigator may increase the dose of thyroid replacement therapy if needed
- Stable doses of inhaled, intra-articular, or topical corticosteroids
- Estrogen (with maintenance of the same dose and route of estrogen administration throughout the trial in case of oral estrogen therapy. In case of non-oral estrogen therapy, the dose may be adjusted as required, but the route of administration must be maintained throughout the trial)
- Contraceptive methods (with maintenance of the same dose and route of estrogen-containing contraceptives throughout the trial)
- Testosterone
- Metformin and DPP-4 inhibitors. Any diabetes treatment other than nutritional counseling, metformin and DPP-4 inhibitors are prohibited at trial entry and discouraged throughout the trial. Dose-optimization of metformin and/or DPP-4 should be the first attempt in case of increasing glucose and/or HbA1c levels during the trial. In case optimized doses of metformin and/or DPP-4 are no longer expected to provide adequate glycemic control, the investigator is strongly encouraged to contact the Medical Monitor to discuss additional treatment options before adding additional medication which could influence the primary endpoint

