9.9.2.2. Prohibited Therapies and Procedures

- Weight-reducing program, diets (unless indicated for diabetes treatment), drugs or appetite suppressants, including orlistat, zonisamide, lorcaserin, bupropion, topiramate, sibutramine, stimulants (eg, phentermine or ADHD medications such as methylphenidate or amphetamines), and GLP-1 receptor agonists (eg, dulaglutide, exenatide, liraglutide, lixisenatide, semaglutide) unless indicated for diabetes treatment (see Section 9.9.2.1)
- hGH therapies other than lonapegsomatropin and the daily somatropin product

- GH secretagogues (permitted if used in connection with stimulation tests for diagnosis of GHD [eg, macimorelin])
- Anabolic steroids other than the therapies described in Section 9.9.2.1
- Bariatric surgery
- Biotin > 0.03 mg/day from supplements. Higher doses of biotin may result in interference with commonly used biotinylated immunoassays and leading to false results
- Cabergoline above 0.5 mg weekly or bromocriptine above 20 mg weekly due to their effects on lowering IGF-1 and GH hormonal concentrations and their independent effects on weight (Abs, 1998; Korner, 2003; Thorner, 1975)

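### The Per-Protocol exclusion list in SAP 10.4 does not match protocol 9.9.2.2: it leaves out prohibited weight-reducing programmes and diets, and it labels GLP-1 use for diabetes a protocol deviation

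*SAP*

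**What the plan says.** SAP 10.4 builds the Per-Protocol set by subtraction from the ITT population: "This set will exclude subjects with the following protocol deviation during the trial". One of the listed deviations is use of prohibited therapies or procedures, followed by a specific sub-list. That sub-list contains anti-obesity drugs and appetite suppressants (with an exception when prescribed for another indication), "GLP-1 receptor agonists (even if indicated for diabetes mellitus)", other hGH products and GH secretagogues, bariatric surgery, anabolic steroids other than testosterone, and cabergoline or bromocriptine above set weekly doses. A separate eligibility criterion reads "Violates major inclusion or exclusion criteria (inclusion 02,03,04 or exclusion 07,15,18)".

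Protocol 9.9.2.2 is the source list of prohibited therapies. Its first item begins "Weight-reducing program, diets (unless indicated for diabetes treatment), drugs or appetite suppressants" and ends with "GLP-1 receptor agonists (eg, dulaglutide, exenatide, liraglutide, lixisenatide, semaglutide) unless indicated for diabetes treatment". Protocol 9.9.2.1 allows whatever is not listed as prohibited. It says that diabetes treatments other than nutritional counselling, metformin and DPP-4 inhibitors "are prohibited at trial entry and discouraged throughout the trial", and it strongly encourages contact with the Medical Monitor before adding medication that could influence the primary endpoint.

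The Per-Protocol set is used in Sensitivity Analysis 1 (SAP 12.10.4) and in the baseline summaries (SAP 12.6). Protocol section 14 makes the final SAP the analysis of record.

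**The concern.** A Per-Protocol analysis is read as the result in subjects who followed the protocol. Here the membership rule and the protocol disagree in both directions.

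A subject who joined a weight-reducing programme breached the protocol in a way that acts on body fat, the quantity being measured. Nothing in 10.4 names that breach, so the subject stays in the set unless withdrawn from the trial or caught by another criterion. A subject who was given a GLP-1 agonist for diabetes after entry did something the protocol discourages but does not prohibit, yet 10.4 counts it as a deviation.

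What is at stake is the meaning of one sensitivity analysis offered as a check on robustness, and the accuracy of how its exclusions would be reported.

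**Working it through.** **Step 1. The two lists side by side.**

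| Item | Protocol 9.9.2.2 | SAP 10.4 | Agreement |
|---|---|---|---|
| Weight-reducing programme | Prohibited | Not listed | No |
| Diets | Prohibited unless indicated for diabetes treatment | Not listed | No |
| GLP-1 agonist for diabetes | Exempt (9.9.2.1: discouraged after entry) | Listed as a deviation | No |
| Weight-loss drugs, appetite suppressants | Prohibited; the only exemption in the item is for diabetes treatment | Exempt for any indication other than weight loss or obesity | Partly |
| Biotin above 0.03 mg/day | Prohibited | Not listed | No |
| GH secretagogues | Prohibited, with an exception for diagnostic stimulation tests | Listed, without that exception | Partly |
| Anabolic steroids | Prohibited, other than therapies in 9.9.2.1 | Listed, other than testosterone | Broadly |
| Other hGH, bariatric surgery, cabergoline and bromocriptine limits | Prohibited | Listed | Yes |

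**Step 2. Does another 10.4 criterion cover programmes and diets?** The remaining criteria are treatment non-compliance, a missing Week 38 DXA, named eligibility violations, and withdrawal before Week 38. The eligibility line names inclusion criteria 02, 03 and 04. The criterion that concerns weight reduction is inclusion 08 ("no weight reduction program intended during the trial or within the last 90 days prior to or through screening"), which is not named. Withdrawal would remove a programme user, since protocol 7.3.1 allows withdrawal for a protocol deviation, but nothing requires it.

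**Step 3. The plan's own figure.** Inputs from SAP section 5: 80 per arm, difference 1.9, SD 3.7, two-sided 5%. SE = 3.7 × √(2/80) = 0.585; 1.9/0.585 − 1.960 = 1.288; power = Φ(1.288) = 0.901. A noncentral t calculation gives 0.898. The stated 90% reproduces, and this point does not affect it.

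**Step 4. How far could the Per-Protocol estimate move?** The documents give no counts, so three quantities are assumptions: k subjects wrongly kept (or removed), all in one arm; f, the number of SDs by which they differ from the rest of that arm; and n, the subjects per arm in the set, counting those k.

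Shift in the arm difference = k × f × 3.7 / n, and SE = 3.7 × √(2/n).

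| n per arm | k | f | Shift (points) | As % of 1.9 | Shift/SE |
|---|---|---|---|---|---|
| 70 | 1 | 0.5 | 0.026 | 1.4 | 0.04 |
| 70 | 1 | 1 | 0.053 | 2.8 | 0.08 |
| 70 | 4 | 0.5 | 0.106 | 5.6 | 0.17 |
| 70 | 4 | 1 | 0.211 | 11.1 | 0.34 |
| 60 | 4 | 1 | 0.247 | 13.0 | 0.37 |
| 80 | 4 | 1 | 0.185 | 9.7 | 0.32 |
| 94 | 4 | 1 | 0.157 | 8.3 | 0.29 |

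The SEs are 0.676, 0.625, 0.585 and 0.540 for n = 60, 70, 80 and 94. The last n is 282/3, from the expected total enrolment in SAP section 2.

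**Step 5. Direction.** If programme users lose trunk fat, keeping them on placebo shrinks the difference and keeping them on lonapegsomatropin enlarges it. The documents give no reason to expect more of them in one arm.

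**The case against.** The strongest reply concerns the GLP-1 line. Its wording shows that the authors knew of the diabetes exemption and set it aside. Protocol 14.4.1 leaves the details of the per-protocol analysis to the SAP, section 14 gives the SAP precedence, and a Per-Protocol set may be stricter than the conduct rules. The remark in 9.9.2.1 about medication that could influence the primary endpoint supplies a plausible reason. All of this stands: the exclusion is a legitimate analysis choice. What it does not justify is calling the use a prohibited therapy and a protocol deviation.

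It can also be said that 10.4 refers to any prohibited therapy and so imports the whole of 9.9.2.2. But a specific list follows, it differs from 9.9.2.2 on several items, and the GLP-1 conflict remains on either reading.

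Some stronger readings are tempting but not supported:

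- **That SGLT-2 inhibitors must be treated like GLP-1 agonists.** Exclusion criterion 15 groups them ("SGLT-2 inhibitors (eg, canagliflozin, dapagliflozin, empagliflozin, sotagliflozin)"), but for use up to screening. 9.9.2.2 does not name them, and no section requires one rule for both classes.
- **That these are the only two departures.** Step 1 shows others: biotin, weight-loss drugs used for other indications, and the secretagogue test exception.
- **That a programme user can never leave the set.** Withdrawal or another criterion may remove the subject.
- **That the set could be built in two conflicting ways, from the deviation log or from concomitant medication.** 10.4 states its own GLP-1 rule outright, and the deviation plan cited in SAP 12.4 is not among the documents.

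**Conclusion.** The point holds as a mismatch between two lists. The substantive half is the omission of weight-reducing programmes and diets: run as written, 10.4 can keep subjects whose breach acts directly on the endpoint. The GLP-1 half is a labelling conflict, and describing that use as freely permitted would also go too far, because 9.9.2.1 discourages it.

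The size is small: about 1 to 3% of the 1.9-point design difference for one subject, and about 6 to 11% for four in the same arm, with 70 per arm. These figures rest on assumed counts, an assumed 0.5 to 1 SD departure, and all affected subjects in one arm; only the SD of 3.7 and the 1.9 come from the plan.

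A reader might infer that the efficacy conclusion is biased. The documents do not support that. The primary analysis uses the ITT population under a treatment-policy strategy and is unchanged, as is the testing sequence. Only Sensitivity Analysis 1 and the Per-Protocol baseline summaries are affected, and no direction of bias is established. This is a worthwhile tidy-up, not a defect in the confirmatory analysis.

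**What to change.** Before unblinding, make two changes to SAP 10.4:

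1. Add the protocol 9.9.2.2 item on weight-reducing programmes and diets, in the protocol's wording and with its diabetes exemption, with subjects identified from recorded protocol deviations.
2. Reconcile the GLP-1 line with protocol 9.9.2.1 and 9.9.2.2, for example by describing it as an additional endpoint-related analysis exclusion and not as a protocol deviation.

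The cost is a few lines, at a time when 10.4 already commits to identifying the set and its criteria before unblinding. A few more subjects may leave the set. Detection is the weak spot: protocol 9.9.2 defines concomitant therapy as medication, so a programme or diet will be found only if it was recorded as a deviation.

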10.5. SAFETY ANALYSIS SET

The Safety analyses will be performed using the Safety analysis set. The Safety analysis set is defined as all randomized subjects who have received any amount of trial drug and will be analyzed by the actual treatment received (not the randomized treatment). If a subject received more than one type of treatment during the trial, such subject will be analyzed by the treatment group the subject received more of.

10.6. PHARMACOKINETIC/PHARMACODYNAMIC (PK/PD) ANALYSIS SET

The PK/PD analyses will be performed using the PK/PD analysis set. This set will include all subjects in the Safety Analysis Set who have PK/PD assessments.

11. DATA SCREENING AND ACCEPTANCE

11.1. GENERAL PRINCIPLES

Data will be reviewed periodically. Any questionable data will be reported to the clinical data manager promptly for query and resolution. The observed data will be reported as is in listings. Imputed data will be used for summary analysis.

11.2. HANDLING OF MISSING AND INCOMPLETE DATA

Missing clinical outcome data can occur for multiple reasons, including missed subject visits and scales or measures with missing item scores. Missing and incomplete data will be identified through the data review plan for this trial. Missing and incomplete data will be identified for investigation, and possible resolution by Data Management prior to the trial database lock or snapshot.

Unless specified otherwise, only the observed data (not imputed data) will be presented in listings.

11.2.1. Missing Birth Dates

To impute missing birth date, the following rules will be applied:

- If day is missing, impute 15.
- If month is missing, impute June.
- If year is missing, then no imputation will be done; the date will be missing.

11.2.2. Missing Medical History Related Dates

- If only day is missing, impute 1.
- If month is missing, impute January 1st.
- If year is missing, then no imputation will be done; the date will be missing.

If the imputed date is earlier than the birth date, then the birth date will be used.

11.2.3. Missing Dates in Adverse Events

For determination of treatment-emergent adverse event (TEAE), if the start date and time of an AE are partially or completely missing, the AE will be assumed to be treatment-emergent if it cannot be definitely shown that the AE did not occur or worsen on or after the first dose in the trial (worst case approach).

The following rules will be used for TEAE determination where the AE has a missing start date.

If the start time of an AE is missing, but the start date is complete, an AE will only be excluded from treatment-emergent AEs if the start day is before day of first treatment or the start day is after end of study day.

If the start time and day are missing but the start month is complete, an AE will only be excluded from treatment emergent AEs if the start month is before the month of first treatment or the start month is after the end month of end of study month or if the stop date/time is before the start of first treatment date.

If the start day and month are missing but the start year is complete, an AE will only be excluded from treatment-emergent AEs if the start year is before year of first treatment or if the start year is after end of study year or if the stop date/time is before the start of first treatment.

If the start date is completely missing, an AE will not be excluded from treatment emergent AEs unless the stop date/time is before the start of first treatment.

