8.2. PREMATURE SUBJECT WITHDRAWAL

Early withdrawal occurs when an enrolled subject ceases participation in the trial, regardless of the circumstances, prior to the expected completion of the trial (= completion of Week 38).

Additionally, the investigator may discontinue the treatment of a subject at any time if considered to be in the subject's best interest, see Section [7.3.1](#) for detailed definition.

If in any case treatment should be discontinued, all subsequent visits and assessments should continue as planned. If the only option for the subject is to drop-out of the trial, the subject may also be offered to only attend the final Visit 7.

If the subject withdraws from the trial prematurely, a Completion Visit/Early Termination Visit should be performed to collect data, particularly AE follow-up data (if applicable), and to collect blood for laboratory evaluations. This visit should contain all assessments from Visit 7 (Week 38, see Schedule of Events, Section [18.2](#)) and will be documented in the eCRF together with the reason(s) for trial withdrawal. Individual assessments may be waived if the subject refuses to participate, if they have been done recently and/or are not deemed appropriate or required. Such instances shall be discussed with the Medical Monitor. For subjects who discontinue the study drug for reasons related to safety, unblinding of the treatment assignment for the subject may occur if deemed necessary by the Sponsor to assess a potential safety signal or by the investigator to provide adequate medical care to the subject.

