12.3.2. Recording Procedures for All Adverse Events

All AEs will be documented in response to questions about the subject’s well-being and whether any possible changes in well-being have occurred since the previous visit. Additionally, at each visit, site staff will review subject diary data with the subject, to determine if diary entries reflect any AEs.

AEs, including SAEs, will be documented through the end of the subject’s participation in the trial or Early Termination visit. All AEs must be recorded on the appropriate CRF. AEs either observed by the investigator or reported by the subject must be recorded regardless of causality. The following attributes must be documented for each reported AE:

- Subject ID
- AE Term
- Description (for SAEs)
- Onset date (if AE was present on Day 1, include whether onset was prior to or after the first dose of the study drug)
- Resolution date, if applicable
- Severity

- Causality (relationship to the study drug)
- Outcome
- Action taken
- Determination of “seriousness criteria” (whether serious or not serious)

Any medical history condition, signs, symptoms, and illnesses active during the Screening Period will be captured as baseline (pre-existing) events, if appropriate, to assure that any change(s) in these experiences during the trial also are recorded as an AE and a complete safety profile is obtained. An event that occurs after signing of ICF but prior to the first study drug administration will be documented as medical history unless the event is trial procedure-related, in which case it will be reported as a non-treatment-emergent AE. Any new or worsening pretreatment event that occurs from the time of the first study drug administration until the last visit will be recorded as an AE.

Routine titration of chronic, concomitant medications will not be considered to meet the criteria for AEs. In addition, increased IGF-1 levels requiring study drug dose decrease (ie, IGF-1 SDS > 2.0) will not be considered as AE. However, occurrence of clinically significant symptoms/conditions associated with increased IGF-1 levels will be considered as AE.

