12.12.1. Adverse Events

Adverse events will be coded by system organ class (SOC) and preferred term (PT) using the Medical Dictionary for Regulatory Activities (MedDRA) Version 26.0 (the most current March version of the dictionary).

An AE (classified by preferred term) will be considered a treatment emergent adverse event (TEAE) if it occurred on or after the first dose of investigational product and was not present prior to the first dose, or it was present at the first dose but increased in severity during the trial through 14 days after the last dose of treatment on the main period or the date of first dose on the extension period whichever occurs first.

- Summary of TEAEs by treatment
- TEAEs by treatment, SOC and PT (sorted by descending frequency by SOC and PT)
- TEAEs by treatment, SOC and PT Reported by > 5% of subjects in any treatment group
- Related TEAE by treatment, SOC and PT
- Serious TEAEs by treatment, SOC and PT (sorted by descending frequency by SOC and PT)
- Serious Related TEAEs by treatment, SOC and PT (sorted by descending frequency by SOC and PT)
- AEs leading to death by treatment, SOC and PT (sorted by descending frequency by SOC and PT)
- TEAEs leading to discontinuation of trial by treatment, SOC and PT (sorted by descending frequency by SOC and PT)
- TEAEs leading to discontinuation of treatment by treatment, SOC and PT (sorted by descending frequency by SOC and PT)
- TEAEs by treatment and PT (sorted by descending frequency of PT)
- Related TEAEs by treatment and PT (sorted by descending frequency of PT)
- Serious TEAEs by treatment and PT (sorted by descending frequency of PT)
- Deaths by treatment

Detailed listings for all AEs, serious TEAEs, AEs leading to the discontinuation of trial, TEAEs leading to the discontinuation of treatment, AEs leading to death and special situation will also be generated.

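### The SAP rule for adverse events with a start date but no start time ignores the 14-day limit on treatment-emergent events and the Day 1 pre-dose field; the effect is probably small and confined to descriptive safety tables

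*SAP*

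**What the plan says.** SAP 11.2.3 opens with a worst-case principle: where the start date or time is partly or wholly missing, an AE is taken as treatment-emergent unless it can be shown not to have occurred or worsened from the first dose onward. It then gives a specific rule: "If the start time of an AE is missing, but the start date is complete, an AE will only be excluded from treatment-emergent AEs". Just two grounds for leaving an event out are then named: "if the start day is before day of first treatment or the start day is after end of study day". The month-only and year-only rules use end of study in the same way. The SAP does not define end of study day.

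SAP 12.12.1 defines a treatment-emergent AE (TEAE) as one where "it occurred on or after the first dose of investigational product and was not present prior to the first dose", or one already present that "increased in severity during the trial through 14 days after the last dose of treatment on the main period", with the first extension dose as the limit if it comes sooner.

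Among the attributes that protocol 12.3.2 requires for every AE is "Onset date (if AE was present on Day 1, include whether onset was prior to or after the first dose of the study drug". No onset time is listed. An event between consent and first dose goes to medical history unless it is procedure-related, "in which case it will be reported as a non-treatment-emergent AE".

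For subjects who stop drug, protocol 8.2 says that "all subsequent visits and assessments should continue as planned".

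**The concern.** SAP 11.2.3 is meant to resolve unknown timing. Its rule for a complete date without a time also overrides timing that is known. The word only leaves two grounds for exclusion. Neither is the 14-day or first-extension-dose limit of 12.12.1, and neither is the Day 1 before/after-dose field that the protocol requires.

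The rule may reach many records. If the eCRF follows the attribute list in protocol 12.3.2, with a date and no time, then a complete date without a time is an ordinary record. The eCRF is not in the documents, so this remains a possibility.

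Safety and tolerability is the first secondary objective, and most of the AE tables in SAP 12.12.1 depend on the TEAE flag. Two programmers, one following 11.2.3 and one following 12.12.1, could flag the same record differently.

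**Working it through.** The plan states no figure on this point, so there is none to reproduce. The check applies the two rules to the same record and then counts the days on which they disagree.

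**Two test records**

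- Last dose on Day 100, subject stays in visits, AE starts on Day 200, no time. Under 12.12.1 the window closes on Day 100 + 14 = Day 114, so this is not a TEAE. Under 11.2.3, Day 200 is neither before Day 1 nor after the end of study, so it is a TEAE.
- Procedure-related AE on Day 1, field says before first dose, no time. Protocol 12.3.2 calls it non-treatment-emergent, and 12.12.1 requires that the event was not present before the first dose. Under 11.2.3 the start day is not before the first treatment day, so it is a TEAE. Such events can occur, because protocol 10.2.2.1 and 10.2.2.2 place almost all Visit 1 assessments before dosing.

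**Days on which the rules disagree**

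Inputs: Day 1 is the first dose and Week 38 is Day 267 (SAP Table 2); Week 42 is 267 + 28 = Day 295. Last-dose days and end-of-study days are assumptions. Excess days = end-of-study day − (last-dose day + 14).

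| Subject | Last dose | End of study | Excess days |
|---|---|---|---|
| Weekly arm, completer, no extension | 263 | 295 | 295 − 277 = 18 |
| Daily arm, completer, no extension | 266 | 295 | 295 − 280 = 15 |
| Stops drug, stays to Week 38 | 78 | 267 | 267 − 92 = 175 |
| Stops drug, stays to Week 38 | 22 | 267 | 267 − 36 = 231 |
| Stops after first dose, stays to Week 38 | 1 | 267 | 267 − 15 = 252 |

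With the 12.12.1 limit written into 11.2.3, every entry becomes 0. For extension entrants the excess depends on what end of study means; it is nil if that is no later than the first extension dose.

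**Upper bound on events**

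The documents give no discontinuation rate and no AE rate. The figures below assume both, and also assume that all AEs are still collected after a subject stops drug.

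Share of an arm's follow-up in the excess window = p × (266 − stop day − 14) / 266, where p is the proportion stopping and 38 × 7 = 266:

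- p = 5%, stop Day 150: 0.05 × 102 / 266 = 1.9%
- p = 8%, stop Day 100: 0.08 × 152 / 266 = 4.6%
- p = 15%, stop Day 60: 0.15 × 192 / 266 = 10.8%

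For one subject stopping on Day 100, at an assumed 2 AEs per year:

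- extra events: 2 × 152 / 365 = 0.83
- chance of any TEAE by Day 114: 1 − exp(−2 × 114 / 365) = 0.465
- chance of any TEAE by Day 266: 1 − exp(−2 × 266 / 365) = 0.767

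The rise from 46% to 77% applies to that one subject. With 8% of an arm stopping then, the arm's TEAE incidence rises by 0.08 × (0.767 − 0.465) = 0.024, or about 1.9 subjects in 80.

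**The case against.** **AE collection stops first.** Protocol 12.2.1 ends AE reporting two weeks after the last dose, or at study discontinuation if earlier; after that only SAEs attributed to prior treatment are to be reported. Schedule footnote c, in both documents, also ends collection two weeks after the last dose, or at Visit 7 for extension entrants. This largely stands. It makes the event figures upper bounds and leaves mainly drug-attributed SAEs in the excess window. It does not empty that window. Protocol 12.3.2 documents AEs to the end of participation, 8.2 keeps subjects who stop drug in visits, and 10.2.5 places an AE review call two weeks after Visit 7. In the weekly arms Visit 7 is 4–5 days post-dose, so that call comes about 18–19 days after the last dose.

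**The 14 days may apply only to worsening events.** The sentence in SAP 12.12.1 can be read that way, and new-onset events would then have no stated upper limit. The usual reading closes the whole window. The ambiguity is a further reason to state one limit.

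**The lead-in already covers the Day 1 field.** A recorded pre-dose onset does show the order, so the worst-case principle would let it exclude the event. That is a fair reading of intent, but the specific rule contradicts it, and the lead-in supplies no upper limit.

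**Over-counting is conservative.** The error does add TEAEs, and safety reporting is descriptive. A worst case is nevertheless meant for unknown order, and here the recorded date or field settles it.

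**Stronger readings.** A reader might infer that the rule governs nearly every AE record, that all off-drug events are miscounted, or that one arm is biased against another. The documents support none of these. The eCRF is not shown, and the reference to a missing start time suggests that a time field may exist. The first 14 days off drug are TEAE time by definition. No discontinuation rates by arm are given.

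**Conclusion.** The rule is wrong as written. SAP 11.2.3 gives a classification that conflicts with SAP 12.12.1 on its usual reading, and with protocol 12.3.2 for procedure-related pre-dose events on Day 1. The effect is probably small. If sites follow protocol 12.2.1, the late events are mainly SAEs attributed to prior treatment; if they follow 12.3.2, more AEs could enter. The 0.83 extra events per stopper and the 46% to 77% rise are ceilings resting on assumed rates and full collection after stopping, and they should not be quoted as expected effects. The Day 1 part is likely a few events at most, because other pre-dose events go to medical history. Only the descriptive safety tables are touched; the primary and key secondary efficacy analyses are not.

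**What to change.** In SAP 11.2.3, replace the end-of-study day, month and year by the day, month and year in which the TEAE period of 12.12.1 ends: 14 days after the last main-period dose, or the first extension dose if earlier. Add that a Day 1 AE is excluded when the recorded field says onset preceded the first dose. Keep the worst-case assumption only where the recorded date and field cannot settle the order.

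In SAP 12.12.1, reword the definition so that the limit plainly applies to new-onset as well as worsening AEs.

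The cost is about two sentences in 11.2.3, a clause in 12.12.1 and one line in the TEAE derivation program, using data that protocol 12.3.2 already requires. The downside is slightly fewer TEAEs in the tables. The late events removed would mostly be drug-attributed SAEs, which would leave the serious TEAE tables but stay in the all-AE listing. If the team wants them tabulated, 12.12.1 should say so directly.
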